In order to enhance sample size for this trial, we will enroll a separate cohort of subjects (ancillary cohort) who are not in the parent trial described above. Women already receiving 250 mg 17-OHPC weekly based on their clinical history will be approached prior to 26 weeks gestation. Eligible subjects either refused the Randomized Controlled Trial (RCT) or they were never approached for the trial. These subjects will be asked to provide two blood samples: one at 26-30 weeks and one 6-9 weeks later to assure steady state. This ancillary study will be implemented initially at the UPITT site only but may be expanded to other sites, as required. Thus, the current design appears to address the challenges described above. Given the observation reported here from the Omega-3 study, it appears that many women receiving 17-OHPC are inadequately treated. It is therefore imperative that this study be performed to establish the relationship between plasma 17-OHPC concentration and the rate of PTB and to determine if higher plasma concentrations will reduce the risk of PTB to a greater degree than reported in the Meis trial. An understanding of the relationship between plasma concentrations of 17-OHPC and PTB rates will lead to an optimized dosing regimen that will benefit a higher

percentage of patients who would otherwise deliver babies prematurely. Preterm birth rate is the only acceptable outcome of interest in assessing the optimal dosing regimen of 17-OHPC as no surrogate biomarker for PTB has been identified at this point. Alternative methods for addressing this problem do not exist.

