8. Does the 17-OHPC concentration in maternal plasma or whole blood correlate better with certain pharmacological and clinical outcomes?

Subjects in the ancillary cohort will already be receiving 250 mg 17-OHPC weekly as part of their standard of care, based on their clinical history. The *primary objective* in the ancillary cohort is identical to the RCT.

The secondary research questions are similar to the RCT except for numbers 2, 3, and 7 above. Data will be collected from subjects in the ancillary cohort, but will not be utilized for secondary research questions 2 and 3 above. These research questions cannot be adequately addressed because subjects in the ancillary cohort are not randomized. Research questions 5 (cord blood only) and 7 cannot be addressed because biological fluids will not be collected at delivery in the ancillary cohort.

C.3. Screening Procedures

All patients who present for prenatal care before 20 6/7 weeks are eligible for screening. The latest gestational age to start treatment in the RCT is 21 6/7 weeks. Subjects who either refuse the RCT or are not approached may be eligible for participation in the ancillary cohort. The inclusion/exclusion criteria will be reviewed with the patient's chart. Potentially eligible subjects will be told about the study and asked to sign a medical records release so that the medical records of her previous deliveries may be obtained. Documentation of the previous deliveries will be reviewed to ensure the patient meets the inclusion criteria. If a patient appears to meet the criteria for enrollment and expresses interest in the study, she will be told about the study and asked to sign the informed consent form. A copy of the consent form will be provided to the patient.

C.3.i. Eligibility Criteria

a. RCT Eligibility Criteria

Inclusion Criteria - Subjects in the RCT must meet all of the following:

1. Pregnant female with documented prior birth between 16 0/7- 35 6/7 week gestation from spontaneous preterm labor or preterm premature rupture of membranes
2. Gestational age (GA) < 22 weeks, based on study determined GA (as treatment must start between 16 0/7 and 21 6/7 weeks)
3. Singleton gestation
4. Age between 18 – 45 years
5. Able to give informed consent and undergo study procedures

Exclusion Criteria - Subjects in the RCT must not meet any of the following:

1. Plan for cerclage
2. Plan for progesterone treatment other than study medication

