10. Known or suspected breast cancer, other hormone-sensitive cancer, or a history of these conditions.
11. Moderately severe depression (PHQ-9 score ≥ 15 , EPDS score of >13 , or suicidal ideation)- based on criteria in the RCT

C.3.ii. Gestational Age Determination

We will use the criteria recommended by the American Congress of Obstetricians and Gynecologists (ACOG)³⁷.

C.4. Informed Consent Procedures and Documentation

Written informed consent will be obtained before entry into the trial. Full disclosure of the nature and potential risks of participating in the trial will be made. Each center will develop its own consent form according to the requirements of its IRB. Women who are not fluent in English will be enrolled by a person fluent in their language and both verbal and written

informed consent obtained in that language; if such are not available, they will not be included.

C.5. Randomization Procedures

Eligible and consenting women will be enrolled and randomized by clinical site and prior preterm birth history (based on earliest SPTB, dichotomized to 30 weeks or less or >30 weeks) to the standard 17-OHPC dose of 250 mg or to a dose of 500 mg intramuscularly weekly starting at 16 0/7 – 21 6/7 weeks and continuing till 36 6/7 weeks gestation. We will stratify at randomization by site and pregnancy history due to the dramatic ethnic, racial and socioeconomic differences in the population at the 3 centers and the demonstrated impact of gestational age at a prior preterm birth on subsequent pregnancy duration. This will be an open label study. Blinding is not required since the primary outcome of interest is the rate of preterm birth according to plasma concentration achieved. Knowledge of the dose by the provider or subject does not impact the primary outcome, i.e., the rate of preterm birth or the plasma concentration. We will not stratify subjects at randomization by any maternal variables since an objective of the study is to define which maternal characteristics might impact 17-OHPC concentrations or efficacy. Our prior work demonstrates a clear impact of maternal BMI but this effect is modest i.e., ~17%.³⁸

Subjects enrolled in the ancillary cohort will not be randomized as they are already on the 250 mg dose.

C.6. Study Procedures

C.6.i. Study Drug Dispensation

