The primary outcome will be the rate of preterm birth (<37 weeks) according to the plasma concentration of 17-OHPC (as a continuous variable) from the 26-30 week sample. The distribution of plasma concentration is expected to be highly positively skewed; thus, a natural logarithmic transformation will be applied to plasma concentrations to produce normally distributed values. A Cox proportional hazard model will be employed to analyze the effect of continuous log-transformed plasma concentration on event-free survival (in this case, “event-free survival” meaning “not birthed until term”). Specifically, the hazard of delivering preterm will be modeled as a function of log-transformed plasma concentration and additional covariates that may influence treatment effectiveness (e.g., BMI, race, gestational age at study entry). Adjusted survival curves will be calculated using the relationship between the hazard function and the survival function. A Wald test will be performed to determine whether the hazard ratio corresponding to a one-unit increase in log-transformed plasma concentration is significantly different from zero. Wald and likelihood ratio tests will also be employed to test for the significance of additional covariates, and stratified analyses may be considered if appropriate (i.e., race-specific analyses). This semi-parametric modeling approach will allow us to analyze the effect of, and not just the presence of, covariates on event-free survival in a robust manner.

Secondary outcomes that are also survival outcomes (such as spontaneous PTB, spontaneous PTB before 32 weeks and before 35 weeks, and indicated PTB) will be analyzed in a similar fashion to the primary outcome analysis described above. For other secondary outcome measures that are continuous variables (maternal and infant hospital days, maternal and fetal plasma concentrations of progesterone, hydroxyprogesterone, 17-OHPC and its metabolite, etc.), linear regression models with appropriate covariates will be utilized.

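### Section D does not say how the non-randomised, 250 mg-only ancillary women enter the primary Cox model, and D.1 names neither randomisation factor as a covariate

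*Combined protocol and SAP*

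**What the plan says.** B.6 states the cohort's purpose: "In order to enhance sample size for this trial, we will enroll a separate cohort of subjects (ancillary cohort". On location it says: "This ancillary study will be implemented initially at the UPITT site only but may be expanded to other sites, as required". C.5 adds: "Subjects enrolled in the ancillary cohort will not be randomized as they are already on the 250 mg dose". No target number of ancillary women is given.

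C.2 says that the primary objective "in the ancillary cohort is identical to the RCT". It then lists the secondary questions these women do not serve. Of questions 2 and 3 (maternal and fetal adverse effects) it says: "These research questions cannot be adequately addressed because subjects in the ancillary cohort are not randomized". C.8 keeps them out of the safety comparison for the same reason.

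C.5 stratifies the RCT randomisation by site and by earliest prior spontaneous preterm birth (SPTB), cut at 30 weeks. The reasons given are: "We will stratify at randomization by site and pregnancy history due to the dramatic ethnic, racial and socioeconomic differences in the population", and "the demonstrated impact of gestational age at a prior preterm birth on subsequent pregnancy duration".

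Neither D.1 nor D.2 mentions the ancillary cohort. D.1 models the hazard of preterm delivery on log concentration from the 26-30 week sample and "additional covariates that may influence treatment effectiveness (e.g., BMI, race, gestational age at study entry". The Cox model comparing the two doses carries the same list. The only stratified analysis mentioned is race-specific, and D.2 names only BMI. Timing of the prior preterm birth otherwise appears only in secondary question 6 (C.2), as a possible modifier of efficacy.

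**The concern.** The primary analysis reads the hazard ratio per unit of log concentration as the drug's effect. Dose drives much of the spread in concentration, and in the RCT dose is balanced over site and prior history by design. Ancillary women break that balance: every one of them is on 250 mg, and at first they come from one site. Pooling them lowers the share on 500 mg at that site. Any difference in preterm birth between that site and the others, or between the cohort and the RCT, then moves with concentration. The protocol says itself that the site populations differ greatly and that prior-birth timing affects pregnancy duration, yet the model is not required to contain either factor.

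The protocol also accepts that lack of randomisation disqualifies these women from two secondary questions and from the safety comparison. It gives no matching rule for the primary question, where the same weakness applies. With an open covariate list in an open-label study, these choices could be made after the data are seen.

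**Working it through.** **The plan's own figure.** D.2 inputs: HR 0.49 per log unit, variance 0.226, 28% preterm, covariates explaining 30% of the variance, 80% power, alpha 0.05. Two-sided, events = (1.960 + 0.842)² / (0.226 × (ln 0.49)²) = 7.85 / 0.1150 = 68.2. So N = 68.2 / 0.28 = 244, and 244 / 0.70 gives 349, against the stated 208 and 296. One-sided gives 192 and 275. The figures do not reproduce. That is a separate issue, and nothing below depends on it.

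**1. How much of the concentration spread is randomised.** Assume that 0.226 is the variance of the 2:1 mix and that concentration is dose-proportional (medians 10 and 20 ng/ml, B.5). The between-dose part is (2/3)(1/3)(ln 2)² = 0.107, which leaves 0.226 − 0.107 = 0.119 within dose, about half. D.2 does not settle the first assumption. The earlier 250 mg cohort in B.5 (median 9.9, 5% above 20 ng/ml) gives a within-dose SD of ln(20/9.9)/1.645 = 0.43, and so a within-dose share of 0.185/(0.185 + 0.107) = 63%.

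**2. Pooling without a site term.** Assumed: 300 RCT women, 90 of them at one site, plus 100 ancillary women at that site.

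- On 500 mg: 60/190 = 32% at that site, 140/210 = 67% elsewhere.
- Gap in mean log concentration: (0.667 − 0.316) × 0.693 = 0.243.
- Pooled variance: 0.119 + 0.25 × 0.480 = 0.239.
- Slope of site on log concentration: 0.475 × 0.525 × (−0.243) / 0.239 = −0.253.
- Log HR per unit with no true effect: ln(site HR) × (−0.253). Site HR 1.5: −0.103, HR 0.90. Site HR 1.2: −0.046, HR 0.955. Site HR 0.67: +0.101, HR 1.11.

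Simulation agrees (10,000 trials per scenario; assumed site shares 30/25/25/10/10% and prior-SPTB HR 1.8 in 40% of women; 28% preterm). BMI and race were not simulated, so the site HR is what remains after adjusting for them.

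| Ancillary women, site HR (no true effect, no site term) | HR per log unit | Rejection |
|---|---|---|
| 100, 1.2 | 0.96 | 6.0% |
| 100, 1.5 | 0.90 | 8.1% |
| 100, 0.67 | 1.10 | 7.2% |
| 50, 1.5 | 0.93 | 6.6% |
| 150, 1.5 | 0.89 | 9.6% |
| 100, half spread over sites, 1.5 | 0.95 | 5.7% |
| 100, 1.5, within-dose SD 0.43 | 0.92 | 7.5% |

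Site strata plus a prior-SPTB term bring these to 0.997-1.005 and 4.8-5.5%. That holds only because no separate cohort effect was simulated.

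**3. A cohort difference under site strata.** Assume cohort HR 1.5 and no site effect. At the shared site the RCT women's mean log concentration is (2/3) × 0.693 = 0.462 higher. The within-site covariance over all 400 women is 0.475 × (100/190)(90/190) × (−0.462) = −0.0547. The within-site variance is 0.239 − 0.249 × 0.243² = 0.225. The slope is −0.244, and −0.244 × 0.405 = −0.099, so HR 0.91. Simulation (1,500 trials) gave 0.90 with 7.8% rejection, and 0.93 with 6.5% for cohort HR 1.3. Only the cohort indicator brings the estimate back to 1.00.

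**4. At the design effect (HR 0.49).** With 100 ancillary women and no site term, the estimate is 0.45 at site HR 1.5 and 0.55 at site HR 0.67. In the latter case power is 87%, against 94% with site strata (3,000 trials).

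**5. RCT women only.** The dose model has power of about 59% without the strata and 61% with them. The concentration model without the strata gives 1.01 and 4.7% if within-dose concentration is unrelated to them. If it were 10% lower in the early-SPTB stratum (assumed), it would give 0.94 and 6.1%.

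**6. Gestational age at entry.** RCT women enter before 22 weeks, near treatment start. Ancillary women may enter up to 26 weeks, already on treatment. If entry is uniform over 16-22 weeks in the RCT and over 18-26 or 20-26 weeks in 100 ancillary women (assumed), it explains 32% or 50% of the cohort indicator, so it acts partly as a cohort marker.

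**The case against.** Use of these women for the primary question is clearly implied: B.6 and C.2 state the purpose and the objective, and C.2 lists the questions they are kept out of. What is missing is how they are used. This stands, and the point is worded accordingly.

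The covariate lists are open examples. Prior-birth timing could qualify under their own test, since secondary question 6 asks whether it affects efficacy, and D.1 provides for testing further covariates. This also stands. A reader might infer that the plan excludes the strata, but it does not; it leaves them optional.

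A reader might also infer that the RCT concentration model is confounded by site or prior history. The documents do not show that. D.2 says that only BMI affects concentration, although D.1 still lists race and co-medications as questions to study. Such confounding is possible but not shown.

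The two groups are also closer in exposure than their entry ages suggest. Both are sampled at trough at 26-30 weeks after at least seven injections (C.6.v), which puts the first ancillary injection at about 23 weeks or earlier. The exposure windows are largely aligned; the entry-age covariate still means different things in the two groups.

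**Conclusion.** The concern holds as a modest, conditional bias and a gap in pre-specification. It arises if ancillary women are pooled without site and cohort terms. With 100 of them at one site, a residual site HR of 1.5 moves a null HR to about 0.90 with about 8% rejection; at 1.2 it is about 0.96 and 6%. The direction depends on whether that site's risk is higher or lower, and spreading the women over sites shrinks the effect. Ancillary numbers, site shares and residual HRs are all assumed, because the documents give none.

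Two stronger readings should be resisted. One is that pooling would undermine a positive result: at the design effect the estimate stays clearly protective. The other is that site strata alone settle the matter: they leave a cohort difference untouched, and a cohort HR of 1.5 still gives about 0.90. For the randomised dose comparison, leaving out the strata costs about two points of power.

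**What to change.** In D.1:

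1. Stratify both Cox models (concentration and dose) by site, and adjust for the earliest-prior-SPTB stratum (cut at 30 weeks).
2. State how the ancillary women are used. If they are pooled, report the RCT-only estimate beside the pooled one, and also the pooled model with an RCT/ancillary indicator.
3. Replace gestational age at study entry by gestational age at first 17-OHPC injection.

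This takes a few sentences and little or no new data: site and prior history are randomisation factors, and secondary question 6 already needs gestational age at treatment start. The cost is precision. With 100 ancillary women and site HR 1.5, the simulated SE of the log HR goes from 0.194 to 0.202 (about 4%) with site strata and prior SPTB, and to 0.217 (about 12%) with the indicator as well. Both remain below the 0.240 from the RCT women alone.

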of 37% (Figure 4). Importantly, only 50% of the women in this study achieved plasma concentrations > 10 ng/ml and only 5% of subjects achieved concentrations greater than 20 ng/ml (Figure 3). The median concentration of 17-OHPC at the highest quartile was only 15 ng/ml (Figure 4). These data suggest that the rate of preterm birth could be reduced further with higher plasma concentrations of 17-OHPC. The higher concentrations could impact two aspects of 17-OHPC efficacy. First, the percentage of women below what appears to be the lowest level of efficacy, i.e., 10 ng/ml would be increased with a higher dose. Secondly, the apparent plateauing effect may disappear with more concentrations in excess of 20 ng/ml. If indeed there is no plateauing of efficacy at higher concentrations, then the overall success rate could be increased beyond the reported 33% overall efficacy of 17-OHPC. This study provided proof of the efficacy of 17-OHPC because the pharmacodynamic end point, PTB was dependent on plasma 17-OHPC concentrations. This evidence addresses those skeptics of the utility of 17-OHPC in preventing recurrent preterm birth.

Using data from the Omega-3 study, we are able to model 17-OHPC pharmacokinetics. Figure 7 depicts plasma concentrations expected from both a 250 and 500 mg weekly dose of 17-OHPC. With the higher doses of OHPC in the proposed study, we anticipate that plasma concentrations will range from ~ 4 - 110 ng/ml with a median concentration of 10 ng/ml with the 250 mg dose and 20 ng/ml with the 500 mg dose based on these simulated data.

Figure 7. Simulated concentrations of 17-OHPC (with 95% CI) following weekly injections of either 250 or 500 mg.

B.6.

Rationale for Proposed Study

Clearly, research that evaluates the dose/ concentration relationship between 17-OHPC and PTB rates is urgently needed. Such a study should correlate a measure of drug exposure such as steady state trough plasma concentrations with the outcome of preterm birth. The potential benefit of identifying a therapeutic concentration range and of optimizing the dosage of 17-

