We will also compare preterm birth rates between treatment groups (250 or 500 mg). Descriptive statistics will be generated for key characteristics of the treatment groups at baseline. For continuous variables, we will report means and standard deviations or medians and interquartile ranges (the latter in the case of skewed distributions or large outliers). Counts and percentages will be reported for categorical variables. We will then construct a Cox model and produce adjusted survival curves to assess the magnitude of differences in PTB rate

between groups while adjusting for covariates that may influence treatment effectiveness (e.g., BMI, race, gestational age at study entry).

We have previously performed population pharmacokinetic analysis of 17-OHPC in twin and singleton pregnancies. In this study, we will also use population pharmacokinetic analysis to evaluate the contribution of various covariates to the observed variability in the trough plasma concentrations of 17-OHPC, a surrogate measure of drug exposure.

D.2. Sample Size and Power

A Cox proportional hazards regression model will be used to assess the effect of log-transformed 17-OHPC concentration on event-free survival, while adjusting for covariates such as maternal BMI.

The recruited cohort of women will be sufficiently large to provide a wide range of drug exposures and enable evaluation of several potential covariates on plasma concentration of 17-OHPC and to describe the association between plasma concentration of 17-OHPC and its efficacy. Based on the large variation in 17-OHPC concentrations we have reported in clinical trials with the standard dose, we are confident that the range of concentrations of 17- OHPC that will be achieved with the two doses selected will provide a sufficiently wide range (between 4 and 112 ng/ml) to enable the performance of a robust concentration response assessment (Figure 7). Based on these simulated data, we estimate that 99% of subjects will achieve a concentration > 10 ng/ml with the 500 mg/week dose.

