Based on the simulated distribution of 17-OHPC plasma concentration at higher doses in this study, we expect the variance of log-transformed concentration to be 0.226. Given the results of the prior study, we have estimated the hazard ratio corresponding to a one-unit increase in log-transformed 17-OHPC concentration to be 0.49. We also anticipate that 28% of study participants will deliver preterm. Thus, a Cox regression based on a sample of 208 women will have 80% power at the $\alpha=0.05$ significance level to detect a hazard ratio of 0.49. This sample size will be adjusted for the presence of other covariates in the Cox model; assuming that additional covariates such as BMI account for 30% of the variation in log-transformed plasma concentration, we require a sample size of **296 women** to achieve 80% power (Table 1). Our

published data indicate that only maternal BMI affects plasma concentrations of 17-OHPC and accounts for no more than 30% of the variation in plasma concentrations (Figure 7). We will recruit 300 subjects overall to account for non-compliance or non-collection of plasma for analysis of 17-OHPC. Data from non-compliant subjects will not be used for any analysis related to plasma 17-OHPC concentration. In addition, data analysis related to plasma 17-OHPC concentration in those subjects who stop 17-OHPC treatment because of a drug allergy, thrombosis or cholestatic jaundice will not be utilized, but their outcomes will be kept and included in the secondary outcomes that are not related to plasma 17-OHPC concentrations. The sample size will be sufficient to address secondary outcomes since the variation in the variables studied will be far smaller than the variation in plasma 17-OHPC concentration.

All three centers have recruited very well in other studies of 17-OHPC from the MFMU. The pool of subjects annually available for recruitment will exceed 300. Even at a study acceptance rate as low as 30%, there are more than enough subjects to enable us to reach our recruitment goal. We anticipate an acceptance rate closer to 50%. All power analyses were performed using PASS 13. [CITE: PASS 13 Power Analysis and Sample Size Software (2014). NCSS, LLC. Kaysville, Utah, USA, ncss.com/software/pass.]

Table 1. Total Sample Size Required for 80% Power

		% variation accounted for by additional covariates			
		0%	10%	20%	30%
% participants delivering preterm	26%	223	248	279	319
	27%	215	239	269	307
	28%	208	231	259	296
	29%	200	223	250	286

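### D.2's stated variance of 0.226 gives 244 and 349 women, not the printed 208 and 296, which fit a variance of about 0.266; one of them must be corrected

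*Combined protocol and SAP*

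**What the plan says.** Section D.2 lists its inputs in one paragraph. On the spread of exposure: "we expect the variance of log-transformed concentration to be 0.226". It takes a hazard ratio of 0.49 for each one-unit rise in log concentration, expects 28% of participants to deliver preterm, and sets alpha at 0.05. It concludes that "a Cox regression based on a sample of 208 women will have 80% power at the" 0.05 level. It then allows for covariates: "assuming that additional covariates such as BMI account for 30% of the variation in log-transformed plasma concentration, we require a sample size of" 296. Table 1 repeats 208 and 296 in its 28% row and gives 14 other combinations of event rate and covariate R². The target of 300 rests on the 296. PASS 13 is named as the software.

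Section D.1 specifies a natural logarithm and a Wald test for a difference. That implies a two-sided test, although D.2 does not state the sidedness.

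Other figures bear indirectly on the spread of concentrations. Section B.5 anticipates "a median concentration of 10 ng/ml with the 250 mg dose and 20 ng/ml with the 500 mg dose". For the earlier 250 mg cohort it reports that "only 5% of subjects achieved concentrations greater than 20 ng/ml" and "The median concentration of 17-OHPC at the highest quartile was only 15 ng/ml". In D.2, "we estimate that 99% of subjects will achieve a concentration > 10 ng/ml with the 500 mg/week dose".

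**The concern.** The required number of women is inversely proportional to the variance of log concentration. The stated variance therefore has to lead to the stated sample size, and it does not.

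This paragraph and its table are the only power justification for the primary objective. The recruitment target exceeds the stated requirement by just 4 women (300 − 296), so it has no room for an error in the variance. As written, a reader cannot tell whether 300 women give 80% power or about 74%. The difference matters most if no concentration-response relationship is found, which is a real possibility: section B.6 itself cites a study that could not demonstrate one.

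**Working it through.** **Inputs.** From D.2: variance of log concentration 0.226; hazard ratio 0.49, so (ln 0.49)² = 0.5089; event rate 0.28; alpha 0.05; power 80%; R² of 0 or 0.30. Taken as two-sided from D.1: (1.960 + 0.8416)² = 7.849.

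**Formula** (Cox regression, continuous covariate):

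N = 7.849 / [variance × (ln HR)² × event rate × (1 − R²)]

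**With the stated variance, 0.226**

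- R² = 0: 7.849 / (0.226 × 0.5089 × 0.28) = 243.7, so 244. Printed: 208.
- R² = 0.30: 243.7 / 0.70 = 348.2, so 349. Printed: 296.
- Ratios: 208/244 = 0.85 and 296/349 = 0.85.
- Cells of Table 1 reproduced: 0 of 16.

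**With 0.266**

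- R² = 0: 207.1, so 208.
- R² = 0.30: 295.8, so 296.
- Table 1, rounding up: 15 of 16 cells exact. The other is 224 against a printed 223 (26% preterm, R² = 0).

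Solving each of the 16 cells for the variance gives 0.2648 to 0.2660. Rounding up, values from 0.26603 to 0.2661 reproduce all 16 cells; rounding to the nearest whole number, 0.26544 to 0.26547 does. The table was therefore built with this formula, and under either convention with a variance near 0.266 if the hazard ratio was 0.49.

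**Other readings of 0.226**

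| Reading | Unadjusted | R² = 0.30 |
|---|---|---|
| One-sided alpha 0.05 | 192 | 275 |
| 0.226 is the within-dose variance (between-dose part (2/9)(ln 2)² = 0.107, total 0.333) | 166 | 237 |
| Printed in D.2 | 208 | 296 |

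A leftover 1:1 allocation would change the between-dose variance by (ln 2)² × (1/4 − 2/9) = 0.013. The gap to explain is 0.266 − 0.226 = 0.040.

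**Power at R² = 0.30**, from Φ(√[N × 0.28 × variance × 0.70] × |ln 0.49| − 1.960)

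| Women | Variance 0.226 | Variance 0.266 |
|---|---|---|
| 296 | 73.3% | 80.0% |
| 300 | 73.9% | 80.5% |

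Simulated Cox models (4,000 runs, 2:1 lognormal mixture, a covariate with R² = 0.30) gave 75% against 81% for 296 women and 76% against 82% for 300. The gap is again about 6 points.

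With 0.226, 300 women reach 80% power only if R² is at most 1 − 243.75/300 = 18.75%, or, at R² = 0.30, if the hazard ratio is about 0.4637 or lower.

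**Do the plan's other figures settle the variance?** Assume lognormal concentrations with equal spread at both doses, 2:1 allocation, and medians of about 10 and 20 ng/ml. The between-dose part is then 0.107.

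- 99% above 10 ng/ml at 500 mg: SD = ln 2 / 2.326 = 0.298, total variance 0.20.
- Top-quartile median of 15 ng/ml at 250 mg: total variance 0.23 to 0.24.
- 5% above 20 ng/ml at 250 mg: total variance 0.28 to 0.29.

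The ranges come from taking the 250 mg median as 10 or 9.9 ng/ml. These values fall on both sides of the two candidates and do not decide between them.

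**The case against.** The strongest objection is that the plan's own table points to a one-digit misprint. If the run used 0.266, then 208, 296, Table 1, the target of 300 and the 80% power all stand. That is the likelier explanation, but nothing in the documents confirms it, and only the sponsor holds the simulation output and the PASS run.

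The variance is also not the only input that could be moved. Table 1 fixes only the product of the variance and (ln HR)², so 0.226 with a hazard ratio of about 0.461 would also fit. This is formally correct. However, D.2 states 0.49 twice and B.5 gives it as the source estimate, so the variance is the input that does not fit. A different event rate is excluded because Table 1 labels its rows.

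The 74% is arguably pessimistic. The 30% is the plan's upper bound for covariate R², the simulation gives 76%, and the ancillary cohort described in B.6 is meant to enlarge the sample and shares the primary objective (C.2). These points stand as qualifications. But 30% is the value on which D.2 bases its 296, and the ancillary cohort has no stated size, so it cannot be counted.

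The lognormal benchmarks are weak evidence. They assume equal spread at both doses, and the upper value of 112 ng/ml in D.2 lies more than 4 SD above the 500 mg median under that model for either variance. That is fair, and the conclusion does not depend on them.

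**Conclusion.** The concern holds. With D.2's own inputs and a two-sided test, 0.226 leads to 244 and 349 women. The printed 208 and 296 need a variance of about 0.266. No reading of the stated inputs that was tried reconciles them.

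The size depends on which figure is true. With 0.226, the printed numbers are about 15% too small, 300 women fall 49 short of the 349 required, and power is about 74%. With 0.266, power is about 81% for 300 women and the error is a single digit. These figures take R² = 30%, a hazard ratio of 0.49 and 28% preterm as D.2 does, and concern only the 296 to 300 women named there.

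Because the figure sits in the only power statement for the primary objective, it must be corrected whichever case applies.

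**What to change.** Keep 300 women. Confirm from the simulation output or the PASS run which variance was entered, then restate D.2.

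- **If 0.266 was used:** correct the printed variance. The sample sizes, Table 1 and the 80% power stand. Cost: one digit.
- **If 0.226 was intended:** replace 208 and 296 with 244 and 349, state about 74% power for 300 women at R² = 30%, and replace Table 1 with the values below. Cost: a rewritten paragraph and table and a less favourable stated power.

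| Preterm | R² 0% | 10% | 20% | 30% |
|---|---|---|---|---|
| 26% | 263 | 292 | 329 | 375 |
| 27% | 253 | 281 | 316 | 362 |
| 28% | 244 | 271 | 305 | 349 |
| 29% | 236 | 262 | 295 | 337 |

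In the second case, C.5 puts the effect of BMI at about 17% without defining the measure. If the sponsor means a share of variance, 243.7 / 0.83 = 293.7, so 294 women would suffice, and D.2 should say that this is the R² it relies on.

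In either case, check the claim that 99% exceed 10 ng/ml at 500 mg. Under the lognormal assumptions above, 0.226 implies about 98% and 0.266 about 96%. Neither branch adds patients.
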